Partners Human Research Committee
Detailed Protocol
Version: 12/17/2019

Project: A Randomized Controlled Trial: EVENup Orthotic Shoe Lift Intervention during CAM Walker Boot Treatment of Nonoperative Ankle Fractures

I. Background and Significance

A variety of foot and ankle injuries can be treated effectively through the use of a controlled ankle movement (CAM) walker boot.¹⁻⁵ CAM walker boots protect the injured area by restricting foot and ankle motion, providing a stable platform to distribute forces while bearing weight, and allowing the user to rollover the foot during ambulation because of a rocker bottom-shaped sole.⁶ Such qualities lend the CAM walker boot to provide ankle support that can be advantageous compared with other commonly used methods.⁷ Despite their utility, CAM walker boots create a simulated leg-length discrepancy (LLD)⁶, which can result in altered biomechanics during ambulation.^{8,9} Additionally, a LLD can be associated with lower back and joint pain.¹⁰

We have previously conducted a study that suggests a relationship exists between CAM walker boot treatment and pain at sites other than the extremity being treated.⁶ There have been several randomized controlled trials (RCTs) examining a relationship between the correction of inherent LLD with insole inserts and lower back pain.^{11,12} Furthermore, there has been a past RCT¹³ and there is a current RCT¹⁴ examining a relationship between the use of the EVENup orthotic shoe lift¹⁵ to correct CAM walker boot simulated LLD and pain at sites other than the extremity being treated. However, these studies were not conducted with patient populations with uniform injuries. To the best of our knowledge, an RCT has not been conducted with the EVENup orthotic shoe lift to examine this relationship in a uniform patient population with nonoperative ankle fractures. This RCT aims to assess the efficacy of the EVENup orthotic shoe lift, towards reducing and even preventing such pain that may be associated with this common course of treatment.

II. Specific Aims

Controlled ankle movement (CAM) walker boot treatment may result in contralateral and ipsilateral lower extremity and lower back pain, due to creating a simulated leg-length discrepancy (LLD). We hypothesize that intervention with the EVENup orthotic shoe lift may prevent or reduce the intensity of pain that can occur during and persist after the course CAM walker boot treatment. We will address our hypothesis through completing the aims listed below:

AIM 1. Prospectively identify and enroll a population of patients with nonoperative ankle fractures that require CAM walker boot treatment in an RCT at Brigham and Women's Hospital, Brigham and Women's Faulkner Hospital, BWH/MGH Health Care Center at Foxborough, [name], and [name]. Patients assigned to Group I, the

control group, will receive standard-of-care treatment with a CAM walker boot. Patients assigned to Group II, the intervention group, will wear an EVENup orthotic shoe lift on the contralateral foot, in addition to receiving standard-of-care treatment with a CAM walker boot for the ankle fracture.

AIM 2. Evaluate the differences in pain that are experienced by patients in the two groups. The pain explored will include that experienced as contralateral or ipsilateral lower extremity joint pain or low back pain while wearing a CAM walker boot, as well as pain that persists at these secondary sites, following the termination of CAM walker boot treatment.

III. Subject Selection

Pending approval from the Institutional Review Board (IRB) and patient informed consent, we will prospectively identify 100 patients with a nonoperative ankle fracture that necessitates treatment with a CAM walker boot during clinic at Brigham and Women's Hospital, Brigham and Women's Faulkner Hospital, BWH/MGH Health Care Center at Foxborough, [name], and [name].

All patients enrolled in the study must have an injury that requires wear of a CAM walker boot for at least six weeks and have ambulation ad libitum without other aids (e.g. crutches, canes, scooters, wheelchairs, etc.). Patients will be excluded from the study if they are a recent post-operative patient for lower extremity injury, have an additional acute injury to a lower extremity or back other than the foot or ankle injury being treated by the CAM walker boot at the time of initiation of treatment, have an ongoing or history of lower extremity joint injury, arthritis, or back pain or have restricted weightbearing as instructed by a physician (i.e. for ankle fracture that cannot weight bear). Additionally, pregnant women and non-English speaking patients will not be eligible for this study.

IV. Subject Enrollment

Subjects will be included in this study if they are eligible to receive treatment with a CAM walker boot for a nonoperative ankle fracture, for a period of at least six weeks. Once the patient is deemed eligible for the study because of their injury, the physician will ask if the patient is interested in hearing more regarding the research study we are conducting. If the patient agrees, the study staff will explain in depth the study aims and protocol during the office visit. At this time, the study staff will consent the patient, and it will be made clear that the patient will be able to rescind their participation at any time during the study for any reason, and that this will not impact their continued care at the Brigham Foot and Ankle Clinic. Brigham Foot and Ankle physicians will be available for any additional questions if needed. The study staff will stress that the study is voluntary, provide all information regarding alternate treatment options, and remind patients that even if they do consent, they will have the opportunity to withdraw participation at any time for any reason. Any subjects who agree to participate will then be asked to fill out questionnaires as a means to obtain initial data.

All patients who consent will be randomly divided into two equal sized groups (n=50) — Group I and Group II. We will randomize our patients using a random number generator. Group I will be randomized to receive CAM walker boot treatment and Group II will receive CAM walker boot treatment with the EVENup orthotic shoe lift as an intervention. Cross-over will not be explicitly offered between the groups, but if participants in Group I utilize an orthotic shoe lift of their own volition, this will be documented. All participants will be evaluated using an intention-to-treat (ITT) approach, where each subject will be analyzed according to their randomization assignment, regardless of actual treatment received.

V. Study Procedures

Initial Visits:

Initial data taken for all patients at the time of enrollment will include demographics (age, sex, race, medical co-morbidities, medications, BMI, smoking history), injury or diagnosis being treated, history of lower extremity pain or low back pain (i.e. hip, knee, back pain), history of lower extremity or low back surgery or injury (i.e. hip or knee replacement, prior fracture) and functional outcome scores using the following surveys:

- Foot and Ankle Ability Measure (FAAM) pertaining to the injured foot or ankle
- Visual Analog Scale (VAS) of pain for each lower extremity joint or low back (low back, right / left hip, knee, ankle, foot, other)

Patients in Group I will be assigned to receive a course of CAM walker boot treatment for a period of six weeks.

Patients in Group II will be assigned to receive a course of CAM walker boot treatment with an EVENup orthotic shoe lift to be worn on the contralateral foot for a period of six weeks.

The opportunity for crossover from Group I to Group II will be permitted if patients develop severe pain. These patients can attempt to remediate their pain by using an EVENup orthotic shoe lift, which are readily available for their purchase in a variety of settings.

Follow Up Assessments:

With regard to clinic visits, all patients in Groups I and II will be seen in the clinic at six weeks to assess the outcomes of the prescribed treatments. Visits will occur at any of the previously mentioned clinic sites. If the fracture has not completely healed, previously prescribed treatment may be extended until healing has been deemed achieved at subsequent follow up visits. Total duration of the prescribed treatment will be recorded for each patient. Additionally, alternative treatment options may be utilized at the physician's discretion if healing has not been achieved with a CAM walker boot. This cohort of patients will not further progress in the study.

Outcomes:

Outcomes for both Group I and Group II will be taken at initiation of boot wear, at six weeks after initiation of the boot, at twelve weeks after initiation of the boot, and at twenty-four weeks after initiation of the boot. We will use the following surveys to measure the outcomes of our patients:

- Foot and Ankle Ability Measure (FAAM) pertaining to the injured foot or ankle
- VAS of pain for each lower extremity joint or low back (low back, right / left hip, knee, ankle, foot, other)

Initial data and all outcome scores will be obtained from subjects using the web-based Partners affiliated Research Electronic Data Capture (REDCap) (Vanderbilt University, Nashville, TN). Use of REDCap will either be done in person on Partners approved devices with the guidance of study staff, or from home using an email-based system of delivery. The latter will require the obtaining of email addresses from subjects and the sending of encrypted study materials securely with the 'send secure' function. Participants can also receive unencrypted emails if they acknowledge the risks, and that Partners will not be held responsible.

VI. Biostatistical Analysis

We will prospectively identify patients who have been diagnosed with nonoperative ankle fractures that require CAM walker boot treatment, at the previously stated clinic sites. Through a one-sided power analysis, with an alpha = 0.05 and 80% power, we determined that a minimum of 42 participants would be needed to be enrolled in each group to detect a 40% reduction in CAM walker-boot associated pain, compared with a previously reported occurrence of associated pain in 67% of patients.⁶ For this reason, we aim to enroll 100 patients in this study, with 50 patients in each of the two arms. Any patients over the age of 18, regardless of gender or ethnicity, who fit the previously stated criteria will be recruited. The study will end after 100 subjects are enrolled.

The primary outcome measurements will be the change in VAS of pain at secondary sites and FAAM from the start of prescribed treatment to six weeks after initiation of bootwear. Our secondary outcome measurements will be the change VAS of pain at secondary sites and FAAM at twelve weeks after initiation of the boot, and at twenty four weeks after initiation of the boot. We will use an ITT approach, where each subject will be analyzed according to their randomization assignment, regardless of actual treatment received. We will use a t-test to compare change in outcome measurements between the two arms.

Patient responses to the VAS and FAAM forms will be collected via REDCap. All statistical analysis and data accumulation will be performed using Microsoft Excel (Microsoft Corporation, Redmond, WA). This includes means, ranges, SD and percentiles.

VII. Risks and Discomforts

Risks to the subject are very minimal. Because this is a prospective study, there is a risk of noncompliance by the patients, for which reason patient cooperation is important. Risks of CAM walker boot wear include the potential for delayed recovery and/or re-injury. There is also previously reported risk of CAM walker boot-associated pain⁶, which we aim to study the reduction or elimination of in this RCT. Additionally, the EVENup orthotic shoe lift increases the elevation of the foot contralateral to the CAM walker boot, although this should not impart any additional risk to patients.

VIII. Potential Benefits

There is no additional benefit to participants in Group I, as they will receive the standard course of CAM walker boot treatment. Potential benefits for participants in Group II include the reduction or prevention of the occurrence of pain, particularly contralateral or ipsilateral lower extremity joint pain or low back pain, due to the simulated LLD compensation provided by the EVENup orthotic shoe lift. If a clinically significant difference is found to exist between treatment arms within this study, these results will guide our future clinical practice in recommending orthotic shoe lifts to patients receiving CAM walker boot treatment.

IX. Monitoring and Quality

The study is not expected to affect the safety of any subjects involved. In order to ensure the safety of subjects, the principal investigator will review all outcome data at the standard follow-up visits and record any adverse events. If adverse events occur, the principal investigator will review the reasonable cause for the event and determine if the research should be altered or stopped.

All data will be collected, viewed, recorded, and analyzed only by study staff listed. The VAS and FAAM measures that the patients will complete at initial visit, six weeks after initiation of the boot, twelve weeks after initiation of the boot, and twenty-four weeks after initiation of the boot data will be recorded in the REDCap database and will be stored on password-protected Partners computers. Only study staff will have access to the digital database.

X. References

2. Preferred Management of Recalcitrant Plantar Fasciitis Among Orthopaedic Foot and Ankle Surgeons - Benedict F. DiGiovanni, Andrew M. Moore, Jason P. Zlotnicki, Stephen J. Pinney, 2012. https://journals.sagepub.com/doi/abs/10.3113/FAI.2012.0507?rfr_dat=cr_pub%3Dpubmed&url_ver=Z39.88-

2003&rfr_id=ori%3Arid%3Acrossref.org&journalCode=faib. Accessed July 30, 2019.

3. Surgery for Type B Ankle Fracture Treatment: a Combined Randomised and Observational Study (CROSSBAT) | BMJ Open. <https://bmjopen.bmj.com/content/7/3/e013298.long>. Accessed July 30, 2019.
4. Tendinopathies of the Foot and Ankle - American Family Physician. <https://www.aafp.org/afp/2009/1115/p1107.html>. Accessed July 30, 2019.

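### The stated 80% power belongs to a comparison of the proportion of patients with pain, which is not planned; it does not apply to the planned t-tests on change in VAS or FAAM

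*Combined protocol and SAP*

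**What the plan says.** All the relevant statements stand in section VI, Biostatistical Analysis, of the combined protocol and SAP.

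- **Sample size.** The settings are given as "Through a one-sided power analysis, with an alpha = 0.05 and 80% power". The plan's resulting requirement reads "a minimum of 42 participants would be needed to be enrolled in each group to detect a 40% reduction in CAM walker-boot associated pain". The reference rate for that reduction comes from an earlier study and is introduced with the words "compared with a previously reported occurrence of associated pain in 67% of patients". Enrolment is then set at 100, or 50 per arm.
- **Primary outcomes.** "The primary outcome measurements will be the change in VAS of pain at secondary sites and FAAM from the start of prescribed treatment". The end of the interval is week six.
- **Test.** "We will use a t-test to compare change in outcome measurements between the two arms". No other between-arm test is named, and its sidedness is not given.

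Section V, Study Procedures, describes the two instruments. Pain is recorded as "VAS of pain for each lower extremity joint or low back (low back, right / left hip, knee, ankle, foot, other". Function is recorded with the "Foot and Ankle Ability Measure (FAAM) pertaining to the injured foot or ankle". The section gives no rule for combining the site-level VAS scores and no cut-off that would turn a VAS score into pain present or absent.

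The hypothesis in section II, Specific Aims, is that the lift "may prevent or reduce the intensity of pain that can occur during and persist after the course CAM walker boot treatment". It therefore covers both whether pain occurs and how severe it is.

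**The concern.** The sample size is built on a yes/no outcome per patient, while the primary analysis compares mean changes on two scales. A power figure holds for one test, one outcome and one assumed effect; it does not pass to a different test on a different outcome. A 40% fall in the share of patients with pain does not fix a difference in mean VAS, because that difference also depends on how severe the pain is, how much it varies, and whether the lift reduces severity. For FAAM there is no link: it scores the injured foot or ankle, whereas section I, Background and Significance, describes the study cited for the 67% as concerning pain away from the treated extremity.

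What is at stake is how the result is read. Section VIII, Potential Benefits, says a clinically important difference between arms will guide practice, but the plan defines none for VAS or FAAM. If a primary t-test is not significant, a reader who trusts the 80% may take this as good evidence of no useful effect. The plan gives no basis for that.

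**Working it through.** **1. Reproducing the 42.** Inputs from section VI: control proportion p1 = 0.67; 40% reduction read as relative, so p2 = 0.67 × 0.60 = 0.402; one-sided alpha 0.05 (z = 1.645); power 0.80 (z = 0.842). With the pooled formula and p̄ = (0.67 + 0.402)/2 = 0.536:

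n = [1.645·√(2·p̄·(1−p̄)) + 0.842·√(p1(1−p1) + p2(1−p2))]² / (p1−p2)²

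= [1.645·√0.4974 + 0.842·√0.4615]² / 0.268² = 41.76, so **42 per arm**.

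The normal-approximation power at 42 is 80.2%. A fall to exactly 40% gives 41.14, also 42. An absolute fall of 40 points (67% to 27%) gives 18.17, so 19; the relative reading is therefore the one behind the plan's figure. A two-sided test would need 53.16, so 54.

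**2. What the plan supplies for the t-test.** A power calculation needs a mean difference, an SD of change, a sidedness and an alpha for each outcome. Section VI gives none of these for the t-test. The only sidedness stated is the one attached to the calculation in step 1. Power for the t-test therefore cannot be computed from the documents, only the standardized difference it could detect.

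**3. Detectable difference with 80% power.** Noncentral t with 2n − 2 degrees of freedom and noncentrality d·√(n/2), where d is the difference in SD units. This assumes one VAS summary score per patient, roughly normal data, equal variances, and n evaluable per arm.

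| Evaluable per arm | one-sided 0.05 | two-sided 0.05 | two-sided 0.025 (alpha split over two outcomes) |
|---|---|---|---|
| 50 | 0.50 SD | 0.57 SD | 0.62 SD |
| 42 | 0.55 SD | 0.62 SD | 0.68 SD |

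Power with 50 per arm, one-sided / two-sided 0.05: true difference 0.4 SD, 63% / 51%; 0.5 SD, 80% / 70%; 0.6 SD, 91% / 84%.

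**4. Can the proportion effect be turned into a VAS effect?** Only with inputs the plan does not give. As an illustration, assume that pain-free patients score 0, that baseline is near 0, and that scores among those with pain have a coefficient of variation between 0.3 and 1.0. For 67% against 40.2%, with 50 per arm and a one-sided test:

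- same severity in both arms: 0.51 down to 0.31 SD, power 81% down to 45%;
- severity 20% lower in the lift arm: 0.73 down to 0.43 SD, power 97% down to 69%.

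The same assumed fall in occurrence is thus compatible with power well below and well above 80%.

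**5. Power if the proportion were tested.** Exact enumeration, 67% against 40.2%:

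| Test | 42 per arm | 50 per arm |
|---|---|---|
| Uncorrected z, one-sided 0.05 | 80% | 85% |
| Uncorrected z, two-sided 0.05 | 74% | 79% |
| Fisher exact, one-sided 0.05 | 74% | 79% |
| Fisher exact, 0.025 per side | 66% | 73% |

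**The case against.** The strongest reply is that no harm has been shown. The mismatch does not bias the estimate or raise the type I error, enrolment already exceeds the calculated minimum, and step 4 shows that a surplus of power is as possible as a shortfall. This stands as far as seriousness goes: it is a statement to correct, not a fault that invalidates the trial. It does not rescue the statement, because enrolling 50 instead of 42 adds power to a test that will not be run and there is still no target for the tests that will be.

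A second reply is that the two-sided figures are not the plan's, since its calculation is one-sided and its hypothesis directional. That is fair. The one-sided figures follow the plan's only stated choice; the two-sided ones are given because the sidedness of the t-test itself is left open.

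A third is that the detectable differences lean on normality. This also stands, for VAS in particular. Section III, Subject Selection, excludes patients with current or past lower-extremity joint injury, arthritis or back pain, so baseline pain at secondary sites is probably low and many changes may lie near zero.

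Two stronger readings are tempting. A reader might infer that the t-tests are underpowered; the documents give no SD or target difference from which to show that. A reader might also infer that patients moved to other treatment are lost to the six-week outcome; section V places that decision at or after the six-week healing assessment, so it does not show such a loss.

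**Conclusion.** The point holds and should be fixed: the power statement is wrong as written for both primary comparisons. The 42 per arm and 80% are arithmetically sound for a one-sided comparison of 67% with about 40% having pain, but that comparison is absent from the analysis plan. For change in VAS the power is unknown rather than low. For change in FAAM no sample-size basis exists.

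The size of the gap can be stated only in SD units, as in step 3 of the working. Those figures rest on full alpha per outcome unless marked as split, on a single VAS score per patient that the plan has yet to define, on the stated number being evaluable, and on a normal approximation that is doubtful for VAS. They cannot be turned into VAS or FAAM points from the documents.

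**What to change.** Keep the outcomes, the t-test and the enrolment, and amend section VI as follows.

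1. Say that the 80% refers to the proportion of patients with pain, and do not present it as the power of the primary t-tests.
2. State whether the t-test is one- or two-sided and whether alpha is split over VAS and FAAM. Replace the power claim for the primary comparisons with the matching detectable differences from the step 3 table, at both 50 and 42 evaluable per arm. State the assumptions with them, including the doubt about normality for VAS.
3. Give the VAS and FAAM differences regarded as meaningful, and an SD of change for each with its source. Divide each difference by its SD and compare it with the detectable value.
4. Optional, if the 67% calculation is kept: add a supporting comparison, ranked below the two primary outcomes, of the proportion with secondary-site pain at six weeks. Fix the VAS cut-off, the sites counted and the test in advance. Quote its power by one method only, for example from the exact figures in step 5. Say that this assumes the 67% applies both to pain present at six weeks and to the sites chosen.

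The cost is protocol wording, with no extra patients or visits; the optional comparison uses VAS data already collected. The downside is that the stated power will no longer cover the primary outcomes. The investigators must also supply an SD and a meaningful difference, which may show that 50 per arm is too few or more than enough.

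### The primary t-test on change is valid, but adjusting for the baseline FAAM and VAS already collected could narrow the confidence intervals at almost no cost

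*Combined protocol and SAP*

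**What the plan says.** Section VI (Biostatistical Analysis) defines the endpoints as change scores, with week 6 as the primary time point: "The primary outcome measurements will be the change in VAS of pain at secondary sites and FAAM from the start of prescribed treatment". Change at 12 and 24 weeks is secondary. The only test named is in the same section: "We will use a t-test to compare change in outcome measurements between the two arms". No section mentions a covariate, a regression or any other adjustment.

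The baseline values exist for everyone. Section V (Initial Visits) lists FAAM and site-by-site VAS under "Initial data taken for all patients at the time of enrollment". Section V (Outcomes) adds: "Outcomes for both Group I and Group II will be taken at initiation of boot wear". The same measurement therefore has four labels: enrolment, initiation of boot wear, start of prescribed treatment (Section VI) and initial visit (Section IX).

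On timing, Section IV says "Any subjects who agree to participate will then be asked to fill out questionnaires as a means to obtain initial data" and then describes randomisation. That suggests baseline comes first but does not say so. Section V (Outcomes) lets the questionnaires be completed in person "or from home using an email-based system of delivery".

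**The concern.** A t-test on change treats the regression of the week-6 score on baseline as if its slope were known to be 1. If the true slope differs, subtracting baseline adds noise that a fitted slope would remove. The treatment estimate stays unbiased, but its confidence interval is wider than the same data allow.

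This matters because the trial is modest in size, with 100 patients planned, and Section VIII says a clinically significant difference would guide the centre's practice. Some patients may also be lost: of those moved to another treatment because the fracture has not healed, Section V says "This cohort of patients will not further progress in the study". The documents give no power for FAAM or VAS change, so no shortfall in power is claimed.

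**Working it through.** **The plan's own figure.** Section VI gives 42 per group: one-sided alpha 0.05, 80% power, and pain in 67% reduced by 40%, so 0.67 × 0.60 = 0.402. With pooled variance and no continuity correction, the mean proportion is 0.536 and

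n = [1.645·√(2 × 0.536 × 0.464) + 0.842·√(0.67 × 0.33 + 0.402 × 0.598)]² / 0.268² ≈ 41.8, rounded up to 42.

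The figure reproduces. It concerns a difference in proportions, so the analysis of FAAM or VAS change does not affect it.

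**Variance comparison.** The inputs r and k (defined as the baseline-to-week-6 correlation and the baseline SD over the week-6 SD) are not in the documents and are assumed. In units of the week-6 variance:

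- change score: 1 + k² − 2rk
- baseline-adjusted regression: 1 − r²
- difference: k² − 2rk + r² = (r − k)²

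The difference cannot be negative, so in large samples adjustment is never less precise. It gains nothing when r = k. Estimating the slope multiplies the adjusted variance by (N − 3)/(N − 4), which is 97/96 = 1.0104 at N = 100 and 81/80 = 1.0125 at N = 84.

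*Example, k = 1 and r = 0.5.* Change: 1 + 1 − 1 = 1. Adjusted: 1 − 0.25 = 0.75. The ratio is 0.750, or 0.758 after the covariate cost. Since √0.758 = 0.871, the interval is about 13% narrower.

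**Power.** The calculation uses the noncentral t distribution with 50 complete patients per arm and an assumed difference of 0.5 week-6 SD. Degrees of freedom are 98 for change and 97 for adjusted. In the example the noncentrality is 0.5/√(1 × 2/50) = 2.50 for change and 0.5/√(0.758 × 2/50) = 2.87 for adjusted. The one-sided column matches the basis of the plan's own power analysis.

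| k | r | Ratio before cost | Ratio after cost | CI width | Power, two-sided 0.05 (%) | Power, one-sided 0.05 (%) |
|---|---|---|---|---|---|---|
| 1 | 0.3 | 0.650 | 0.657 | 19% narrower | 55.3 to 73.3 | 67.5 to 82.7 |
| 1 | 0.5 | 0.750 | 0.758 | 13% narrower | 69.7 to 81.1 | 79.9 to 88.6 |
| 1 | 0.7 | 0.850 | 0.859 | 7% narrower | 89.2 to 93.2 | 94.1 to 96.5 |
| 0.75 | 0.3 | 0.818 | 0.826 | 9% narrower | 65.1 to 73.3 | 76.1 to 82.7 |
| 0.75 | 0.5 | 0.923 | 0.933 | 3% narrower | 78.4 to 81.1 | 86.6 to 88.6 |
| 0.75 | 0.7 | 0.995 | 1.005 | about equal | 93.3 to 93.2 | 96.6 to 96.5 |
| 0.5 | 0.3 | 0.958 | 0.968 | 2% narrower | 71.9 to 73.3 | 81.7 to 82.7 |
| 0.5 | 0.5 | 1.000 | 1.010 | 0.5% wider | 81.6 to 81.1 | 88.9 to 88.6 |
| 0.5 | 0.7 | 0.927 | 0.937 | 3% narrower | 91.6 to 93.2 | 95.6 to 96.5 |
| 0.25 | 0.3 | 0.997 | 1.008 | 0.4% wider | 73.6 to 73.3 | 83.0 to 82.7 |
| 0.25 | 0.5 | 0.923 | 0.933 | 3% narrower | 78.4 to 81.1 | 86.6 to 88.6 |
| 0.25 | 0.7 | 0.716 | 0.723 | 15% narrower | 83.5 to 93.2 | 90.3 to 96.5 |

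Power runs from the change t-test to the adjusted regression. The median ratio after cost is 0.933. If only 42 per arm were complete (an illustration, since no dropout rate is given), two-sided power at k = 1 would go from 48.2 to 65.5, 62.0 to 73.8 and 83.2 to 88.3% for r = 0.3, 0.5 and 0.7.

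**Simulation.** With normal data, 50 per arm, a true effect of 0.5 and 20,000 trials per cell, both estimators averaged 0.499 to 0.503 in every cell. The variance ratios agreed with the table to within 0.01. In separate null simulations, two-sided type I error was 4.8 to 5.2% for the change t-test and 4.7 to 5.2% for the adjusted analysis. Both are valid.

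**Change or follow-up as the response.** On one simulated data set, modelling change and modelling the week-6 value, each with baseline as covariate, gave the same arm coefficient (0.5438) and standard error (0.2015). The baseline slopes were −0.530 and 0.470, which differ by exactly 1.

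**The case against.** The strongest reply is that nothing is wrong: the plan defines change as the outcome, tests change, and the test is valid. That is correct, and it limits the point to a recommendation on efficiency.

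Second, the gain rests on assumed inputs. This also stands. The grid is not a forecast and its median is not an expected gain. The grid stops at k = 1, and larger k would favour adjustment more: at k = 1.5 the ratios after cost are 0.391, 0.433 and 0.448 for r = 0.3, 0.5 and 0.7. But not knowing the slope is itself a reason to estimate it rather than fix it at 1.

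Third, secondary-site VAS may gain little. Section III excludes patients who "have an ongoing or history of lower extremity joint injury, arthritis, or back pain", so baselines may sit near zero with little spread, and the normal-data simulation would not represent them. A simulation with most baselines at zero (8,000 trials at each r) gave ratios of 0.97, 1.00 and 0.98 for r = 0.3, 0.5 and 0.7: little gain, but no material loss. Near-zero baselines are an inference from the exclusions. A small k does not by itself rule out a gain, as the last row of the table shows. The argument does not reach FAAM.

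Fourth, adjustment is not strictly free. It costs about 1% of variance, and three of the 12 cells lose by that much or less.

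Fifth, the patients who leave are those found unhealed at or after the six-week visit, so their week-6 scores may still be obtained. That is a fair reading, and the 42-per-arm figures are conditional for that reason.

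Finally, baseline timing matters to the change score as much as to an adjusted analysis. That is true: a baseline completed after a patient knows the allocation could bias either. Stating the order protects both.

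**Conclusion.** The concern holds as a recommended improvement, not an error. The change t-test is unbiased under randomisation, provided baseline is not influenced by allocation, but it discards information that the trial already collects. In units of the week-6 variance the large-sample loss is (r − k)².

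Its size cannot be derived from the documents. Under the assumed grid it ranges from a loss of about 1% of variance to a gain of about a third. If r and k are close, nothing material is lost by keeping the plan. If they differ appreciably, the interval on a primary outcome is needlessly wide. The documents do not show which of the two primary outcomes would gain more.

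**What to change.** 1. In Section VI, replace the t-test sentence with: *Week-6 FAAM will be compared between arms by linear regression on randomised arm and baseline FAAM; the arm coefficient with its 95% CI is the treatment effect. The same model will be used at 12 and 24 weeks.* Apply the same model to secondary-site VAS once its summary measure is named. Section V records VAS at many sites without a summary score, and the planned t-test needs one too. Because the power analysis is one-sided and a 95% CI corresponds to a two-sided 0.05 test, state which basis applies.
2. Keep the change outcomes and add: *The arm coefficient is identical whether change or the follow-up value is modelled with baseline as covariate.* The change t-test can remain as a sensitivity analysis.
3. Add to Section IV or V: *Baseline FAAM and VAS questionnaires will be completed before the random allocation is made.* Use one label for that baseline in Sections V, VI and IX.

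The cost is one replaced sentence, two added sentences and a consistent label, plus the VAS summary measure and the statement of sidedness. No new data or patients are needed, and Excel, the named software, can fit the regression. The statistical cost is about 1.0% of variance at N = 100 and 1.25% at N = 84. If some patients now complete baseline after allocation, the order of those two steps must change.
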